6.6.2 Primary Efficacy Analysis

The primary efficacy endpoint is the change from baseline in cUHDRS score at Week 101. This is defined as the attribute "variable" of the primary estimand in Section 6.6.1.

Note: The primary efficacy endpoint for the U.S. FDA will be change from baseline in the TFC score at Week 101. TFC will be analyzed the same way as the cUHDRS.

The primary efficacy analysis for this study will compare each active treatment arm, RO7234292 Q8W and RO7234292 Q16W, against the placebo arm.

To account for the multiple comparison, an appropriate procedure will be used to maintain the overall two-sided type I error at 5% (details will be given in the SAP).

The analysis of the primary endpoint will be performed by means of analysis of covariance (ANCOVA). The model will include the corresponding endpoint baseline score, CAG repeat length, baseline CAP score (defined in Section 4.1.1), and treatment as covariates. On the basis of this analysis, least squares mean for the treatment differences at Week 101 and corresponding 95% CIs will be derived.

The robustness of the primary method of estimation described above may be explored by alternative sensitivity estimators based on varying assumptions underlying the multiple imputation strategy. These sensitivity analyses will be described in the SAP.

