Note: The primary efficacy endpoint for the U.S. FDA will be change from baseline in the TFC score at Week 101. TFC will be analyzed the same way as the cUHDRS.

The primary efficacy analysis for this study will compare each active treatment arm, RO7234292 Q8W and RO7234292 Q16W, against the placebo arm. To account for the multiple comparison, an appropriate procedure will be used to maintain the overall two-sided type I error at 5% (details will be given in the SAP).

The analysis of the primary endpoint will be performed by means of analysis of covariance (ANCOVA). The model will include the corresponding endpoint baseline score, CAG repeat length, baseline CAP score, and treatment as covariates; the final list of covariates will be defined in the SAP. On the basis of this analysis, least squares mean for the treatment differences at Week 101 and corresponding 95% CIs will be derived.

The robustness of the primary method of estimation described above may be explored by alternative sensitivity estimators based on varying assumptions underlying the multiple imputation strategy. These sensitivity analyses will be described in the SAP.

Determination of Sample Size

The planned sample size is adequate to capture meaningful clinical decline on both the TFC and cUHDRS and was estimated on the basis of data available from non-interventional studies (TRACK-HD, COHORT, ENROLL-HD) and a randomized placebo-controlled study (2CARE). Based on these data, using the anticipated trial population, a meta-analysis for the change from baseline at 24 months in TFC score suggested a natural decline of 1.36 points and a corresponding pooled standard deviation of 1.78. A conservative treatment discontinuation rate at Week 101 for patients receiving placebo or active is assumed to be 20% and 15%, respectively. Using these assumptions, the simulation described in the protocol was performed to estimate the sample size.

It was estimated that 267 patients per arm will provide approximately 80% power, at a two-sided $\alpha = 0.025$ level, to detect a 40% slowing of clinical decline for RO7234292 as compared with placebo at 101 weeks. This treatment effect translates into an expected average decline of ~ 0.82 points at 101 weeks for the RO7234292 arms. The minimal detectable difference with these assumptions is ~ 0.38 points.

Optional Interim Analyses

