3.3.4 Rationale for Biomarker Assessments

3.3.4.1 Cerebrospinal Fluid Biomarkers

Measurement of protein levels in the CSF offers the potential to monitor molecular changes that take place in the CNS. A toxic gain-of-function mechanism of mHTT protein is widely considered to be the primary driver of disease pathophysiology in HD (Wild and Tabrizi 2017). mHTT protein in human CSF is associated with disease stage and severity and with biomarkers of neuronal damage, including CSF NfL and CSF tau levels (Wild et al. 2015). NfL levels in CSF predict progressive MRI measures of brain atrophy, as well as progressive clinical decline in patients (Wild and Tabrizi 2017). Longitudinal analysis of mHTT, NfL, tau, and other biomarkers related to HD, neurodegeneration, and inflammation in CSF may extend the current understanding of HD pathophysiology and progression and provide further data on how these putatively prognostic and potentially predictive biomarkers will respond to disease-modifying treatment.

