3.3.4.5 Magnetic Resonance Imaging

MRI is a non-invasive method to assess structure and function of the human brain and can provide insights into pathophysiological mechanisms of neurologic and neuropsychiatric disease. Several MRI techniques have shown sensitivity to detect abnormal structure and function within brains of individuals suffering from HD. Structural MRI will be used to assess brain volume, diffusion-weighted MRI will be used to examine structural brain connectivity, and resting-state functional MRI will be employed to identify functional connectivity. All of the measures will be assessed at the whole-brain and regional levels. The acquisition parameters of each sequence, structure, and length of each MRI session and image processing algorithms will be outlined in a separate MRI manual.

Structural Magnetic Resonance Imaging

Numerous structural MRI studies have demonstrated wide-spread brain atrophy, including whole-brain, caudate, and ventricular changes in patients with premanifest and manifest HD (Douaud et al. 2006; Harrington et al. 2016). Brain volume correlates with cognitive function (Peinemann et al. 2005). Further, whole-brain, caudate, and ventricular volumes can predict and track progressive clinical decline in patients with HD

and can also be associated with molecular biomarkers of neurodegeneration, such as NfL (Tabrizi et al. 2012).

Diffusion Magnetic Resonance Imaging

Widespread changes in basal ganglia–cortical structural connectivity have also been observed in patients with HD (Novak et al. 2015), including associations between striatum-sensorimotor cortex connections and UHDRS motor scale and TMS (Bohanna et al. 2011), suggesting that the clinical phenotype in manifest HD may be a result of altered structural connectivity.

Resting-State Functional Magnetic Resonance Imaging

Resting-state functional MRI studies have generated evidence for functional connectivity alterations and their correlation to several clinical and cognitive measures in patients with HD (Werner et al. 2014; Dogan et al. 2015; Liu et al. 2016; Espinoza et al. 2018), implying that disrupted functional integrity of distinct brain networks may underlie clinical progression in HD.

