4.5.6 Laboratory, Biomarker, and Other Biological Samples

Samples for the following laboratory tests will be sent to the study site's local laboratory for analysis:

- Coagulation: INR and/or PT, aPTT, and platelet count
- Urine pregnancy test

Urine pregnancy tests will be performed for women of childbearing potential at specified visits. If a urine pregnancy test is positive, it must be confirmed by a serum pregnancy test (analyzed at a central laboratory).

- CSF for safety: cell count (RBCs and WBCs), glucose, and protein

The following samples will be sent to a central laboratory:

- Hematology: WBC count, RBC count, platelet count, hemoglobin, hematocrit, and differential count (neutrophils, eosinophils, basophils, monocytes, lymphocytes)
- Serum chemistry panel: bicarbonate or total carbon dioxide (if considered standard of care for the region), sodium, potassium, chloride, glucose, BUN or urea, creatinine, total protein, albumin, phosphorus, calcium, total and direct bilirubin, ALP, ALT, AST, uric acid, gamma-glutamyl transferase, and CPK
- Thyroid panel: thyroid-stimulating hormone and free thyroxine (also known as T4) levels
- Viral serology: HBsAg and HCV antibody (or viral RNA if HCV antibody assay is positive)
- Serum pregnancy test

Serum pregnancy tests will be performed for women of childbearing potential at screening. At subsequent visits, it will be performed to confirm a positive urine pregnancy test (if applicable).

- Urinalysis, including dipstick (pH, specific gravity, glucose, protein, ketones, blood) and microscopic examination for all abnormal dipstick results (sediment, RBCs, WBCs, casts, crystals, epithelial cells, bacteria)
- CSF and blood (plasma) samples for PK analyses and metabolite identification
- Blood (plasma) samples for immunogenicity analyses
- Blood sample for determination of CAG repeat length in *HTT* for patient eligibility
- Blood sample for clinical genotyping to look at factors influencing HTT function and severity of the disease
- CSF samples for analysis of mHTT, NfL, and tau levels to evaluate the effects of RO7234292 compared with placebo (primary and secondary biomarker endpoints)
- Blood, plasma, and CSF samples for exploratory research on biomarkers and biomarker assay development

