4.5.7 Magnetic Resonance Imaging

Structural MRI will be used to assess brain volume, diffusion-weighted MRI will be used to examine structural brain connectivity, and resting-state functional MRI will be employed to identify functional connectivity. All of the measures will be assessed at the whole-brain and regional levels. All scans are mandatory unless a site does not have the capability to perform a resting-state functional MRI or diffusion-weighted MRI. For these cases, the Medical Monitor should be consulted; approval to continue without these scans would be required.

The MRI should be performed using a 3-Tesla (3T) magnet. The acquisition parameters of each sequence, structure, and length of each MRI session, as well as image processing algorithms, will be outlined in a separate MRI manual. MRI scans will be managed by a central laboratory to monitor and ensure the integrity and quality of the acquired data. The screening MRI will be evaluated by the central laboratory to determine patient eligibility. Local neuroradiologists will still be responsible for assessing MRI-related ongoing safety monitoring. During central review, the Sponsor and/or site staff will be notified of any unexpected findings requiring clinical follow-up.

MRI should take place as early as possible within the screening window but may take place at any time during screening. The MRI safety and efficacy screening scan will need to pass the central laboratory image QC and the results must be available before the patient can be enrolled in the study.

After patient enrollment at specified timepoints, the MRI must be scheduled to occur before the lumbar puncture (see [Appendix 1](#)). The MRI scan should be performed 7–14 days prior to the lumbar puncture to allow time for re-scanning if the quality of the initial MRI is inadequate. If the re-scan cannot be performed prior to the lumbar puncture, then it can be conducted the day after the lumbar puncture, as long as there are no post-lumbar puncture contraindications and it occurs within 2 weeks of the original scan.

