4.5.9.3 Total Motor Score

The TMS is a holistic measure of motor function in HD that is linked to both functional capacity based on the TFC score, independence, and driving status (Beglinger et al. 2012; Schobel et al. 2017).

The TMS score is the sum of the individual motor ratings obtained from administration of the 31-item motor assessment portion of the UHDRS by the investigator. The score ranges from 0 to 124, with a higher score representing more severe impairment. The TMS takes approximately 15 minutes to administer and will be completed at clinic visits.

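### The covariates listed for the primary ANCOVA leave out baseline CSF NfL and brain volume, which the protocol calls predictors of decline and already collects; adding them is a cheap improvement of unknown size

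*Protocol*

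**What the plan says.** Section 6.6.2 sets the primary model: "The model will include the corresponding endpoint baseline score, CAG repeat length, baseline CAP score (defined in Section 4.1.1), and treatment as covariates". TFC, the primary endpoint for the FDA, is to be analyzed in the same way. The synopsis, under Primary Analysis, gives the same covariates but adds that "the final list of covariates will be defined in the SAP". Section 6.6.2 has no such qualifier, although Section 6.10 does for the biomarker models.

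On prognosis, Section 3.3.4.1 states that "NfL levels in CSF predict progressive MRI measures of brain atrophy, as well as progressive clinical decline in patients", and Section 3.3.4.5 that "whole-brain, caudate, and ventricular volumes can predict and track progressive clinical decline in patients with HD". Section 3.3.4.1 is also cautious, speaking of learning "how these putatively prognostic and potentially predictive biomarkers will respond to disease-modifying treatment". Section 4.5.9.3 describes the TMS as "linked to both functional capacity based on the TFC score, independence, and driving status".

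These measures are available before treatment:

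- Section 4.5.6 provides for "CSF samples for analysis of mHTT, NfL, and tau levels to evaluate the effects of RO7234292 compared with placebo", and Appendix 1a schedules a CSF sample at baseline.
- For MRI, Section 4.5.7 requires that "The MRI safety and efficacy screening scan will need to pass the central laboratory image QC" before a patient can be enrolled.
- TMS, SDMT and SWR are scheduled at baseline, and the notes to Appendix 1a place assessments before dosing unless otherwise specified.

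**The concern.** CAP is Age × (CAG − 33.66) (Section 4.1.1), so CAG and CAP together carry only age and repeat-length information. Apart from the endpoint's own baseline, the listed model holds no measure of a patient's current neurodegeneration, although the protocol names two kinds and needs their baseline values anyway for the secondary biomarker endpoints (Section 2.5.2).

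The gap is wider for TFC. Baseline cUHDRS already contains TFC, TMS, SDMT and SWR (Section 4.5.9.1). The TFC model has only the baseline of a 5-item scale running from 0 to 13.

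In a randomized comparison, a prespecified prognostic baseline covariate in a linear model lowers residual variance without meaningful bias, at the cost of a few degrees of freedom. Narrower intervals are useful whether the trial shows benefit, no effect or harm. The primary estimator also runs on multiply imputed data (Section 6.6.1), and predictors of decline in the imputation model make its missing-data assumption more plausible.

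**Working it through.** **Inputs from the protocol (Sections 6 and 6.2).** 267 patients per arm; two-sided alpha 0.025 per comparison; power about 80%; Week 101 TFC decline 1.36 on placebo and 0.82 on active, a difference of 0.54; SD 1.78; discontinuation 20% on placebo and 15% on active; unadjusted t-test on 20 imputed datasets; minimal detectable difference about 0.38.

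**Reproducing the plan's figures.** Repeating the Section 6.2 simulation with 5,000 replicates gave 79.7% power at 267 per arm, against the stated 80% or so. The minimal detectable difference with completers at 80% and 85% of 267 is

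2.2414 × 1.78 × √(1/213.6 + 1/226.95) = 0.380,

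which agrees with the stated value. No covariate enters either figure, so the stated power does not depend on the covariate list.

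**Effect of extra covariates.** Let R² be the share of the remaining variance that the added covariates explain beyond those already listed. The protocol gives no value, so R² is an assumption.

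- Standard error ratio = √(1 − R²)
- Power from an 80% start = Φ[(2.2414 + 0.8416)/√(1 − R²) − 2.2414]
- Equivalent extra patients per arm = 267/(1 − R²) − 267

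| Assumed R² | SE ratio | Power from 80% | Equivalent extra patients per arm |
|---|---|---|---|
| 0% | 1.000 | 80.0% | 0 |
| 3% | 0.985 | 81.3% | 8 |
| 5% | 0.975 | 82.2% | 14 |
| 10% | 0.949 | 84.3% | 30 |
| 15% | 0.922 | 86.5% | 47 |

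The same simulation with residual variance reduced gave 84.7% at R² = 10% and 86.2% at 15%, in line with the formula.

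**Dependence on the starting point.** The 80% belongs to an unadjusted test. The planned ANCOVA starts higher to the extent that its own covariates are prognostic, and the increments then shrink. Suppose, purely for illustration, that the listed covariates already explain 10%. Power starts at 84.3%, and a further R² of 15% of what remains gives

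Φ[3.0830/√(0.90 × 0.85) − 2.2414] = Φ(1.284) ≈ 90.0%,

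a gain of about 5.7 points rather than 6.5. The standard error ratio does not depend on the starting point and is the safer summary.

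**The case against.** The strongest objection is that nothing here is an error. The synopsis leaves the final covariate list to the SAP, which is not shown. Baseline score, CAG and CAP are a defensible prespecified set, and the planned power needs no covariate at all. This stands: a reader might infer that the list is closed or that the power statement is too high, and the documents support neither.

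A reader might also infer that precision is certainly being lost. That is not shown. Only the variance explained beyond the listed covariates counts, no document gives it, and Section 3.3.4.1 itself treats the prognostic value of these markers as putative. A gain near zero is possible.

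The TFC part is weaker still. Section 4.5.9.3 reports an association of TMS with functional capacity, not prediction of later change, and nothing comparable is said of SDMT or SWR. Adding the three is harmless, but the benefit is less well supported.

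The power figures assume 40% slowing over a full course of treatment, whereas dosing stopped on 22 March 2021 after unfavorable trends. The reduction in standard error does not depend on that scenario; the power points do.

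Finally, Sections 3.1.2 and 4.2 of Version 6 unblind the sponsor to treatment assignment, while Section 6 still places unblinding after database lock. Choosing covariates while holding treatment codes invites a charge of data-driven selection. This does not defeat the proposal, but it governs who may fix the list and rules out loose choices among volumes.

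**Conclusion.** This is a cheap improvement, not a correction of an error. Section 6.6.2 lists neither CSF NfL nor any brain volume, although the protocol describes them as predictors of decline and has them before the first dose. For an assumed additional R² of 0 to 15%, the standard error falls by 0 to about 8%, which from 80% power is worth 0 to about 6.5 points, and somewhat less if the listed covariates are themselves prognostic. The conclusion rests on that assumed range and on random allocation with a prespecified linear model. The stated power of about 80% reproduces and is not in question. Separately, Section 6.6.2 and the synopsis should agree on whether the covariate list is final.

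**What to change.** In Section 6.6.2, and in the imputation model of Section 6.6.1:

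- Add log baseline CSF NfL and one named MRI measure, screening caudate volume, to the primary ANCOVA.
- For the TFC analysis, also add baseline TMS, SDMT and SWR.
- Fill a missing baseline covariate with the overall mean across arms, so that no patient is dropped.
- Have the list and transformations fixed and documented by statisticians without access to treatment codes or outcomes by arm.
- Keep the present model as a sensitivity analysis.
- Make the synopsis and Section 6.6.2 consistent on the status of the list.

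The cost is wording in the protocol and SAP, a few missing baseline values to fill, and a slightly longer model. The plan already collects all the measurements.

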6. STATISTICAL CONSIDERATIONS AND ANALYSIS PLAN

All patients enrolled prior to Version 4 of the protocol will not be included for any efficacy analysis. The safety data collected for these patients up to and including the end of treatment visit in Protocol BN40423 will be analyzed separately.

The primary efficacy analysis will be conducted at the end of the study (see Section 3.2). Treatment assignments will be unblinded to the Sponsor at the end of the study after the data have been cleaned and verified and the database has been locked.

Details of the planned statistical analyses mentioned below will be fully specified in a separate Statistical Analysis Plan (SAP), which will be finalized prior to the locking and unblinding of the study database.

Unless otherwise specified, all the p-values considered in Section 6 are two-sided.

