6.2 DETERMINATION OF SAMPLE SIZE

The planned sample size is adequate to capture meaningful clinical decline on both the TFC and cUHDRS and was estimated on the basis of data available from non-interventional studies (TRACK-HD, COHORT, ENROLL-HD) and a randomized placebo-controlled study (2CARE). Based on these data, using the anticipated trial population, a meta-analysis for the change from baseline at 24 months in TFC score suggested a natural decline of 1.36 points and a corresponding pooled standard deviation of 1.78. A conservative treatment discontinuation rate at Week 101 for patients receiving placebo or active is assumed to be 20% and 15%, respectively. Using these assumptions, the simulation described below was performed to estimate the sample size.

Description of Simulations to Derive the Sample Size

The design used for the simulation was simplified to consider only 2 treatment arms (placebo and active) and 2 postbaseline timepoints (Week 49 and Week 101). These simplifications are justifiable given that:

- The overall alpha level 5% will be split to 2.5%, such that each active treatment will be tested against placebo independently. Within each testing chain, a hierarchical procedure will be used to test the primary endpoint and secondary endpoints (see Section 6.3).
- The difference on the derived sample size for considering more than two postbaseline timepoints would be minimal.

The following algorithm was run and repeated 500,000 times:

1. Generate change from baseline values in TFC at Week 49 and Week 101 for N active patients according to the following bivariate normal distribution:

$$\begin{pmatrix} y_{wk49} \\ y_{wk101} \end{pmatrix} = N \left(\mu = \begin{pmatrix} 0.47 \\ 0.82 \end{pmatrix}, \sum = \begin{pmatrix} 1.56^2 & 1.8 \\ 1.8 & 1.78^2 \end{pmatrix} \right)$$

where y_{wk49} and y_{wk101} is the change from baseline in TFC, respectively, at Week 49 and Week 101, μ is the assumed true change at those two timepoints, and Σ is the variance-covariance matrix. Subsequently:

- set to missing, due to study drug-related (SDR) reasons, both values at Week 49 and Week 101 for 5% of the N patients. Set to missing, due to non-study drug-related (NSDR) reasons, both values at Week 49 and Week 101 for additional 2.5% of the N active patients.

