6.3 TESTING STRATEGY AND MULTIPLICITY ADJUSTMENT

The overall alpha level 5% will be split to 2.5% for testing each active treatment against placebo. A hierarchical approach will be used for multiple adjustments that accounts for multiple endpoints (the primary and secondary endpoints).

Within each testing chain (RO7234292 Q8W and RO7234292 Q16W), the endpoint will be tested only if the preceding endpoint is significant at the alpha level 2.5%. Details of the order for secondary endpoints will be detailed in the SAP.

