2. Analysis step: Each of the resulting "m" datasets will be analyzed using the statistical model described in Section 6.6.2, which will provide an estimate of treatment difference.
3. Pooling step: The results from the "m" datasets will be combined (Rubin 1987) leading to an overall estimate of the treatment effect and associated 95% confidence intervals and p-values.

Full details of the algorithm for multiple imputation (e.g., which reference population to use for each missing data pattern, number of imputed datasets, method for imputation, etc.) will be provided in the SAP.

A supplementary estimand may be considered (and will be defined in the SAP).

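### Each dose is tested against placebo at two-sided 2.5%, but the same primary contrast is reported with a 95% interval, so a dose can fail its test while its interval excludes zero

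*Protocol*

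**What the plan says.** Protocol Section 6.3 fixes the level of each test: "The overall alpha level 5% will be split to 2.5% for testing each active treatment against placebo". Section 6.2 gives the same split when justifying the sample size: "The overall alpha level 5% will be split to 2.5%, such that each active treatment will be tested against placebo independently". The opening of Section 6 settles the sidedness: "Unless otherwise specified, all the p-values considered in Section 6 are two-sided".

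The intervals for those contrasts are set at a different level. In Section 6.6.2, and in the same words in the synopsis under Primary Analysis, "least squares mean for the treatment differences at Week 101 and corresponding 95% CIs will be derived". In Section 6.6.1 the imputed datasets are combined, "leading to an overall estimate of the treatment effect and associated 95% confidence intervals and p-values".

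Nowhere does the protocol specify a 97.5% or simultaneous interval for the primary contrasts, or describe the 95% interval as unadjusted or descriptive.

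**The concern.** A two-sided test at level α and a confidence interval at level 1 − α from the same estimate and standard error give the same answer about zero. A 2.5% test therefore pairs with a 97.5% interval. The protocol pairs it with a 95% interval, which is narrower, and the two outputs can disagree: the test says the dose has not shown a difference, while the interval beside it excludes zero. Section 6.6.1 places the intervals next to the p-values from the same pooled analysis, which invites reading one against the other.

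What is at stake is how the primary result is read. A reader who takes an interval that excludes zero as a positive result for that dose would be applying a 5% criterion where the plan applies 2.5%.

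**Working it through.** **Inputs (all from the protocol).** Two-sided alpha per dose 0.025 (Sections 6.2 and 6.3). Interval level 95% (synopsis, Sections 6.6.1 and 6.6.2). Allocation 1:1:1 with one shared placebo arm (Section 3.1.1). On TFC: 267 patients per arm, decline 1.36 on placebo and 0.82 on active, SD 1.78, discontinuation 20% on placebo and 15% on active, power about 80%, minimal detectable difference about 0.38 (Section 6.2). Critical values: z = 1.960 for 95% and z = 2.241 for 97.5%.

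**Step 1: reproduce the plan's figures.** The minimal detectable difference is z × SE.

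- From completers: 267 × 0.80 = 213.6 and 267 × 0.85 = 226.95 patients, so SE = 1.78 × √(1/213.6 + 1/226.95) = 0.170. With z = 2.241 this gives 0.380, the stated ~0.38. With z = 1.960 it gives 0.333.
- From a re-run of the Section 6.2 simulation (8,000 replicates, 20 imputations): power at alpha 0.025 is 79.5%, against about 80% stated. The mean pooled SE is 0.166, giving 0.372 with z = 2.241 and 0.325 with z = 1.960.

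The plan's own detection threshold is therefore the half-width of a 97.5% interval, not of the 95% interval to be reported.

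**Step 2: where test and interval disagree.** The 95% interval excludes zero when p < 0.05; the test succeeds when p < 0.025. They disagree when 0.025 ≤ p < 0.05, that is, when the estimate lies between 1.960 and 2.241 standard errors from zero. With the simulated SE this is 0.325 to 0.372 TFC points, or about 0.33 to 0.37.

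**Step 3: how often, per dose.**

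- No effect: 0.05 − 0.025 = 0.025, or 2.5%.
- Design effect (40% slowing): in the simulation p < 0.05 in 86.9% of replicates and p < 0.025 in 79.5%, so 7.4% fall between. A simpler normal approximation, with the difference diluted by 10% to 0.486 and all 267 patients per arm contributing, gives 88.4% − 81.9% ≈ 6.4%. About 7% is a fair summary.

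**Step 4: joint coverage of the two intervals.** With equal arms and equal variance σ², each contrast has variance 2σ²/n and the shared placebo mean gives covariance σ²/n, so the correlation is 0.5. Joint non-coverage is 1 − P(|Z₁| < c and |Z₂| < c):

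| Interval level | c | Correlation 0.5 | If independent | Bonferroni bound |
|---|---|---|---|---|
| 95% | 1.960 | 9.07% | 1 − 0.95² = 9.75% | 10% |
| 97.5% | 2.241 | 4.65% | 1 − 0.975² = 4.94% | 5% |

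**Step 5: cost in width.** 2.241 / 1.960 = 1.14, so a 97.5% interval is 14% wider.

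**The case against.** The strongest reply is that nothing here is an error of inference. The decision rule rests on p-values: within each chain "the endpoint will be tested only if the preceding endpoint is significant at the alpha level 2.5" per cent. A 95% interval has 95% coverage for its own contrast, and showing unadjusted 95% intervals beside multiplicity-controlled tests is a common display. Much of this stands. It answers any claim about error control, but not the mismatch: the protocol calls the 95% intervals those that correspond to the contrasts tested at 2.5%, and does not label them unadjusted.

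It can also be said that Section 6.6.2 leaves the multiplicity procedure to the SAP. But Section 6.3 already fixes the 2.5% split and three places already fix the 95% level, so two stated figures disagree; this is not a detail left open.

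Three stronger readings are tempting, and the documents do not support them:

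- **That the trial's error rate is 9%.** The 9.1% is the joint non-coverage of two intervals for which the protocol claims no simultaneous coverage. The familywise error of the two primary tests is 4.65% with the shared placebo arm, and at most 5%.
- **That wider intervals are needed to judge harm.** Dosing was stopped after unfavorable trends on active treatment, so readers will look at these intervals for harm. Widening them makes a harmful difference less likely to stand out. The alpha split guards against false claims of efficacy and gives no reason for a stricter standard on harm.
- **That the secondary endpoints need the same change.** Section 6.6.3 states no interval level for them, so no stated figure would be corrected. In a hierarchical chain a secondary endpoint's 97.5% interval can exclude zero although the gate before it has failed, so the change would not reproduce the testing rule.

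**Conclusion.** The point holds as a reporting mismatch in the two primary contrasts. The level of the reported interval (95%) does not match the level of the test it accompanies (two-sided 2.5%), and for p between 0.025 and 0.05 the two give opposite messages about zero. Type I error is unaffected.

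The 2.5% null figure and the 14% width ratio depend only on the two levels. The 9.1% and 4.65% do not depend on the endpoint, but assume a correlation of 0.5 from equal allocation and equal variance. The 7% and the band of 0.33 to 0.37 points are more limited. They are on TFC, from a t-test simulation, under 40% slowing and the planned discontinuation rates. All dosing stopped on 22 March 2021, so those assumptions no longer describe the trial; and Section 6.2 gives no SD for the composite score (cUHDRS) that is the primary endpoint outside the FDA submission. These figures show the size of the mismatch at the planned design and are not a forecast.

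**What to change.** In the synopsis (Primary Analysis), the pooling step of Section 6.6.1 and Section 6.6.2, state that each of the two primary contrasts is reported with a 97.5% confidence interval, matching the per-dose alpha in Section 6.3. Keep the 95% interval only as an additional display, labelled as not adjusted for multiplicity; a reader assessing harm then still has the conventional interval. If the SAP adopts a procedure other than the fixed 2.5%/2.5% split, the interval level should follow that procedure. No change is asked for the secondary endpoints.

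With 97.5% intervals, each primary interval excludes zero exactly when its test succeeds, and joint non-coverage of the pair is 4.65% (at most 5%). The cost is wording in three places, one table column, and primary intervals 14% wider. Tests, sample size and data collection do not change.
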